#### 5.1.2.3 RECTUM: *Per Protocol: V36Gy < 1cc.*

For the HDR component of RTOG 0321, the rectum V75%RxDose constraint was < 1cc. Assuming an  $\alpha/\beta$  ratio of 3Gy for late effects, the EQD1.8 is 30.1Gy. Adding the 45Gy of external beam prescribed in RTOG 0321 yields 75.1Gy, at 1.8Gy/fx. The 5-fraction equivalent dose is 7.12Gy  $\times$  5 = 35.6Gy ( $\alpha/\beta=3$ ). Thus, the 5-fraction constraint equivalent to that used in RTOG 0321 would be V35.6Gy < 1cc

Using the rectal constraint for conformal external beam RT of RTOG 0126 (see table 3), and converting to a 5 fraction equivalent dose ( $\alpha/\beta=3$ ) yields D15 < 36.4Gy. For a rectal volume of 50cc, this is equivalent to V36.4Gy < 7.5cc. The HDR constraint is more restrictive than that of RTOG 0126, thus this protocol adopts a constraint close to the former: rectum V36Gy < 1cc.

#### 5.1.2.4 BLADDER: *Per Protocol: V37Gy < 10cc.*

RTOG 0321 proposed a bladder constraint for HDR delivery as: V75%Rx dose < 1 cc. Despite this restriction, for a small group of UCSF HDR plans, the *average* bladder V80%RxDose was 0.7cc. An attainable HDR constraint would be V80%Rx dose < 1cc. Converting to EQD1.8 using  $\alpha/\beta$  of 3 for late effects, and adding the 45Gy external beam yields a EQD1.8 of 78.6Gy. This is equivalent to 36.6Gy in 5 fractions. Beaumont had no bladder constraint for HDR, and reported minimal chronic bladder toxicity (most was urethral). Using the bladder constraint for conformal external beam RT of RTOG 0126 (see table 3), and converting to a 5 fraction equivalent dose ( $\alpha/\beta=3$ ) yields: D15 < 37.8Gy, or conservatively estimating total bladder volume at 100cc, V37.8 Gy < 15cc. While this 5 fraction dose constraint is similar to RTOG 0321's 5-fraction equivalent of 36.6 Gy, the 15cc volume constraint is far more liberal. Since bladder volumes very substantially, an absolute volume constraint may be preferable to a fractional volume constraint, especially with the rapid dose fall-off seen with CyberKnife. For this protocol, an approximate average of the two RTOG EQDs (37Gy) is used as the bladder dose constraint. A volume constraint of 10cc is approximately midway between 1cc and 15cc.

#### 5.1.2.5 PENILE BULB: *Per Protocol: V29.5Gy < 50%.*

Mack Roach found an increased incidence of impotence when the average dose to the penile bulb was greater than 52.5Gy, conventionally fractionated. This is biologically equivalent to 29.5Gy in 5 fractions, using an  $\alpha/\beta$  ratio of 3Gy. Efforts should be made to minimize the penile bulb V29.5Gy to significantly less than 50%.

#### 5.1.2.6 SIGMOID COLON AND OTHER BOWEL: evaluated if lying within 2cm of the PTV. No more than 1cc may receive the 2Gy/fx equivalent of 54Gy; assuming an $\alpha/\beta=3$ , the 5-fraction equivalent is 30Gy. Thus V30Gy<1cc.

### 5.1.2.7 PROSTATIC URETHRA (when visualized): *Per Protocol: V47Gv < 20%*.

Beaumont's HDR protocol limited "any segment of urethra" to 125% of prescription dose, or 47.5Gy. This is equivalent to 141.3Gy at 2Gy/fx, assuming  $\alpha/\beta$  ratio of 3 for late effects. The 5-fraction equivalent dose is 52.4Gy. RTOG 0321 for HDR delivery required the V125%Rx dose < 1cc. Including the 45Gy of external beam delivered, the  $EQD_{1.8} = 118.6Gy < 1\text{ cc}$ ; the 5 fraction equivalent is 46.4Gy. Since measured diameters of urethras will vary depending on catheter diameter or subjective MRI interpretation, a DVH constraint might best be expressed as a fraction of the total volume. Since 5cc would be a generous estimate for a urethral volume, 20% volume constraint (yielding 1cc, per RTOG 0321) is conservatively chosen. The dose constraint of 47Gy is midway between the Beaumont and RTOG requirements.

#### 5.1.2.8 MEMBRANOUS URETHRA (when identified) *Per*

Protocol: D50 < 37 Gy

Since urethral strictures following HDR often involve the membranous portion, this will be contoured when visualized. Dmax and D50 will be recorded; keep D50 below 37Gy.

**5.1.2.9 NEUROVASCULAR BUNDLE:** If identified, attempt to keep (for both right and left sides) V38Gy<50%.

## 6.0 Study Evaluations

a. Biopsy recommended at 2 yrs if failure suspected, & required at time of documented failure
b. Continue every 6 or 12* months through year 2; upon review at 2 years, investigators may opt to continue annually through year 10.
c. Within 2 – 3 weeks after study entry
d. 5 – 10 days after fiducial placement
e. Either CT or Ultrasound $\leq$ 90 days prior to registration
f. To be performed for nonlocal failure as clinically indicated or deemed necessary by treating physician at any time during follow up

## 6.1 EVALUATION DURING TREATMENT & FOLLOWING TREATMENT

- 6.1.1 PRE-ENTRY ASSESSMENT: see section 4.0.
- 6.1.2 Stereotactic radiosurgery is an outpatient procedure. Patient management immediately after the procedure will follow routine patient care guidelines as determined by the physician. Subjects will be provided instructions on who to call with specific contact information, in the event they experience any untoward effects following treatment. In the event a subject experiences any untoward effects following treatment, information specific to the patient's condition and symptoms, treatment intervention required, and hospital stay and course will be recorded for purposes of clinical evaluation.
- 6.1.3 ACUTE ASSESSMENT: Patients will have toxicity evaluation and AUA score on the last day of treatment.
- 6.1.4 ASSESSMENTS FOLLOWING TREATMENT: at one week after treatment, toxicity and AUA score will be evaluated. At 1 month following treatment, patients will be assessed for acute toxicity, and will fill out AUA form, FACT-G, EPIC-26, SHIM and Utilization of Sexual Rx/Devices. At 3, 6, 12, 18, and 24 month intervals, patients will be seen and evaluated, including a history, physical exam, ECOG performance status, PSA, toxicity evaluation, and AUA score. In addition, at 6 months, 12 months and 24 months, the FACT-G, EPIC-26, SHIM and Utilization of Sexual Medications/Devices will be administered.
- 6.1.5 PROSTATE BIOPSY will be performed at time of biochemical or local clinical failure, and is encouraged at time of distant failure.
- 6.1.6 BONE SCAN will be performed at the time of biochemical failure, or when the patient develops signs of symptoms suggesting metastatic disease.

## 6.2 CRITERIA FOR TOXICITY

- 6.2.1 ACUTE AND LATE TOXICITY (Primary Safety Objectives)
- 6.2.2 Acute side effects ( $\leq$ =90 days of treatment start) will be assessed using the NCI Common Toxicity Criteria version 3.0 (see section 8.2.1).

## 6.3 QUALITY OF LIFE ASSESSMENTS (Secondary Objectives)

- 6.3.1 FACT-G: Functional Assessment of Cancer Therapy - General version of the scale constitutes the core of all subscales. FACT-G can be used with patients of any tumor type. It measures generic health status relevant across different age, disease, and treatment groups. It provides a comprehensive, psychometrically sound

assessment of health status from the patient's point of view by scoring responses to standard questions. The FACT-G is self-administered, and can usually be completed in less than 3 minutes without assistance.

6.3.2 EXPANDED PROSTATE CANCER INDEX COMPOSITE (EPIC)-26: is a validated comprehensive instrument developed to assess patient function and bother after prostate cancer treatment. It was developed by an expert panel of urological oncologists, radiation oncologists (including those with brachytherapy expertise), survey researchers, and prostate cancer nurses, to address symptoms related to radical prostatectomy, external beam radiotherapy, prostate brachytherapy, and hormonal symptoms. See appendix III.

6.3.3 AMERICAN UROLOGICAL ASSOCIATION (AUA) SYMPTOM INDEX: Also known as the International Prostate Symptom Score (IPSS), this widely used index assesses urinary symptom bother. See appendix III.

6.3.4 SEXUAL HEALTH INVENTORY FOR MEN (SHIM): is a widely used, internationally validated and sensitive instrument for assessing erectile dysfunction.

6.3.5 UTILIZATION OF SEXUAL MEDICATIONS/DEVISES: provides context for interpreting the sexual domain score of the EPIC questionnaire.

6.4 CRITERIA FOR DISEASE CONTROL: intervals will be measured from date of first treatment.

6.4.1 (Primary Efficacy Objective) **BIOCHEMICAL DISEASE-FREE SURVIVAL (bDFS)**: is measured as time to PSA failure. While earlier reports of prostate cancer patients treated with radiotherapy have used the ASTRO consensus definition (ACD) of PSA failure, recent studies have suggested the “nadir+2” definition is a more sensitive and specific definition of biochemical failure. Indeed, a recent expert panel met in Phoenix and developed a consensus recommendation using the later definition. So that comparisons can be made with earlier literature, both definitions shall be used:

6.4.1.1 Phoenix definition: failure occurs when the PSA is  $\geq 2$  ng/ml more than the lowest PSA measurement before the current one, with no backdating. Administration of salvage therapy (hormones, surgery, etc...) will be considered failure.

6.4.1.2 Strict ASTRO Consensus Definition (ACD): failure is defined as three consecutive rises in post-treatment PSA, measured at the specified follow-up intervals. If three consecutive PSA rises occur during the first 2 years after treatment, followed by a non-hormonal induced PSA decline, this will not be considered a failure. Administration of salvage therapy (hormones, surgery, etc...) will be considered failure. Failure date is the midpoint between the dates of the last non-rising PSA and the first PSA rise.

6.4.2 CRITERIA FOR **LOCAL FAILURE** (Secondary Objective): clinical evidence of local progression or recurrence. Clinical

failure includes a palpable abnormality that has increased in size, failure of regression of a palpable abnormality by 2 years after treatment, or redevelopment of a prostate abnormality after complete response. Patients with a prostate abnormality compatible with local recurrence, or a PSA failure shall undergo a prostate biopsy. Histologic criteria for local failure is a positive prostate biopsy more than 2 years after treatment. Patients with a normal exam and no evidence of PSA failure shall be considered controlled locally. Patients with clinical failure and no biopsy are

considered local failures. If a patient is locally controlled at the time of orchiectomy or androgen ablation, he is censored and considered “not evaluable” for further local control.

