Given the relatively recent interest in SBRT for prostate cancer (the past 2-3 years), there are only a few institutions that have, to date, reported outcomes following SBRT for prostate cancer. This paucity of data highlights the need for trials such as the one proposed here. With the exception of Virginia Mason Medical Center and Stanford University, the majority of experiences are available in abstract form only. A Phase I/II trial of SBRT at Virginia Mason Medical Center using a linear accelerator and fiducial marker system was reported by Madsen et al.. Forty low-risk patients received 33.5 Gy in 5 fractions (BED2Gy = 78 Gy; a/b = 2 Gy). Six noncoplanar fields using a linear accelerator and daily stereotactic localization of the prostate using three radio- opaque fiducial markers were used. A margin of 4 to 5 mm from block edge to the prostate was used for treatment. Patients were placed on a diet to minimize gas and took daily simethicone to reduce rectal dilatation and movement during treatment. Before each fraction, orthogonal images were obtained and analyzed for the position of the fiducial markers. An automated computer program (Isoloc 5.2; Northwest Medical Physics Equipment, Linwood, WA) was used to calculate the necessary position shifts before treatment. With a median follow-up of 41 months, 4-year PSA nadir + 2 FFBF was 90%, and ASTRO (three rises) FFBF was 70%. Acute Grade 1 or 2 toxicity RTOG toxicity was 49% (genitourinary) and 39% (gastrointestinal). There was a single incidence of Grade 3 genitourinary toxicity. Late Grade 1 or 2 toxicity was 45% (genitourinary) and 37% (gastrointestinal). No late Grade 3 or higher toxicity was reported. At Stanford University forty-one patients received 36.25 Gy in 5 fractions (BED2Gy = 90.6 Gy; a/b = 1.5 Gy). Patients were treated with implantable gold fiducials for daily localization, as well as intrafraction tracking performed every 30–90 s. With a median follow-up of 33 months, no patient has experienced biochemical failure (ASTRO or nadir + 2). There were 2 patients with RTOG Grade 3 late urinary toxicity and none with Grade 3 rectal toxicity. There was no Grade 4 toxicity. The first 21 patients received daily treatment; the remaining 20 patients were treated every other day. Quality of life scored according to the Expanded Prostate Cancer Index Composite suggested improved rectal complications with every-other-day dosing.

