## 2.0 Objective

### PRIMARY OBJECTIVES:

- 2.1 The primary safety goal of this study is to determine, in both low-risk and intermediate-risk cohorts, the rates of acute and late grade 3-5 gastrointestinal and genitourinary toxicity observed during the initial 24 months following hypofractionated SBRT for prostate cancer. Patients will be followed for at least 5 years but possibly as long as 10 years, but initially we will strive to obtain 2 year follow-up results.
- 2.2 The primary efficacy goal is to document the rate of biochemical Disease-Free Survival (bDFS), Phoenix and ASTRO definitions, at 2 years. As above, we will ultimately aim for at least 5 years of follow-up but possibly as long as 10 years, with a short term goal of 2 years.

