## 7.3 STATISITCAL METHODS:

The *primary* objectives of this study are:

- To determine, in both low-risk and intermediate-risk cohorts, the rates of acute and late grade 3 or higher gastrointestinal and genitourinary toxicity observed during an initial 24 month follow up.
- To estimate the rate of biochemical Disease-Free Survival (bDFS), Phoenix and ASTRO definitions, at 2 years following hypofractionated SBRT for low and intermediate risk prostate cancer. Failure occurs when the PSA is  $\geq 2$  ng/ml more than the lowest PSA measurement before the current one, with no backdating.

The *secondary* objectives of this study are to:

- the rate of local failure: proportion of patients with local disease progression at 2 years

- rate of distant failure: proportion of patients with metastatic disease at 2 years
- rate of disease-free survival: median time from start of treatment until disease progression
- rate of disease-specific survival: death due to prostate cancer (excludes patients that relapse with inactive disease)
- overall survival: median length of time from either the date of diagnosis or the start of treatment for a disease, such as cancer, that patients diagnosed with the disease are still alive.
- quality of life (QOL) in generic and organ-specific domains using the FACT-G assessment tool

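### Section 7.3.1.2 does not say whether Phoenix or ASTRO bDFS feeds its single 92% rule, and a 2-year ASTRO rate computed from PSAs through month 24 is biased upward

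*Combined protocol and SAP*

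**What the plan says.** Section 2.2 sets the primary efficacy goal: to "document the rate of biochemical Disease-Free Survival (bDFS), Phoenix and ASTRO definitions, at 2 years". The Protocol Summary and 7.3 repeat it and spell out only one failure rule beside it, the Phoenix rule: "Failure occurs when the PSA is $\geq 2$ ng/ml more than the lowest PSA measurement before the current one, with no backdating". Section 6.4.1 explains why ASTRO is kept: "So that comparisons can be made with earlier literature, both definitions shall be used".

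Under 6.4.1.2, ASTRO "failure is defined as three consecutive rises in post-treatment PSA, measured at the specified follow-up intervals", and "Failure date is the midpoint between the dates of the last non-rising PSA and the first PSA rise". The same paragraph counts salvage therapy as failure. It also cancels three rises within the first 2 years if a decline not caused by hormones follows.

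The PSA schedule is in 6.1.4: "At 3, 6, 12, 18, and 24 month intervals, patients will be seen and evaluated", with PSA among the assessments. Footnote b of section 6.0 leaves visits after year 2 to the investigators' choice, at yearly intervals up to year 10. Section 2.1 says patients are followed for at least 5 years.

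Section 7.3.1.2 calls the treatment effective if the one-sided 95% Wilson lower limit L for the bDFS proportion p is not below 92%. It does not say which definition supplies p, or whether one or both must pass. Section 7.2.2 takes the 92% from 5-year Phoenix results in low-risk men.

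**The concern.** There are two linked faults. First, the only efficacy decision in the plan rests on a proportion whose failure definition is not named, while two definitions are called primary. Whoever runs the analysis would have to choose, possibly with the data in view.

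Second, the two definitions do not become known at the same time. Phoenix failure can be called on the PSA that crosses the threshold and is not backdated, so a month-24 PSA is enough for Phoenix failures through month 24. ASTRO failure needs two further rises after the first and is then dated before the first. Some failures that belong inside the 2-year window are therefore not yet visible when month-24 data are complete. A man with such a failure counts as a success in p, which moves the ASTRO rate towards passing.

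**Working it through.** **1. The plan's own rule and power.** Inputs are n = 200, Z = 1.645 and the bound 92% (7.2.2, 7.3.1.2). With x successes and p = x/n,

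L = [2np + Z² − Z√(Z² + 4np(1−p))] / [2(n + Z²)].

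- x = 191: (384.706 − 10.018)/405.412 = 92.42%, pass.
- x = 190: (382.706 − 10.495)/405.412 = 91.81%, fail.

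The rule therefore needs at least 191 of 200. The exact chance of passing at a true 92% is P(X ≥ 191 | 200, 0.92) = 3.7%. Section 7.2.2 states 99% power at a true 97% (the same sentence also says 80%) and 78% at 96%. The exact values are 91.9% and 71.9%. No single formula tried gave both stated figures. That is a separate matter, and this point does not depend on it.

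**2. Which ASTRO failures can be called, and when.** Date = (last non-rising visit + first rise)/2. Visits through month 24 are from 6.1.4; later visits are annual, per footnote b of 6.0.

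| Last non-rising PSA | First rise | Failure date | Third rise |
|---|---|---|---|
| 3 | 6 | 4.5 | 18 |
| 6 | 12 | 9 | 24 |
| 12 | 18 | 15 | 36 |
| 18 | 24 | 21 | 48 |

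If the pre-treatment PSA is allowed as the reference, one more run appears (rises at 3, 6 and 12), dated month 1.5. So month 9 is the latest date callable from rises alone by month 24. Because 7.3.1.2 uses a simple proportion, the loss comes from needing three rises. The backdating is what places the missed failures inside the 2-year window.

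**3. Effect on the pass rule if ASTRO supplied p.** Assume PSAs only through month 24 for every man and no salvage therapy. Let s be the share of true 2-year failures dated by month 9. The apparent rate at a true 92% is 1 − 0.08s, and the chance of passing is P(X ≥ 191 | 200, 1 − 0.08s). The documents do not give s, so a range is shown.

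| s | Apparent 2-year rate | Chance of passing |
|---|---|---|
| 100% (all seen) | 92.0% | 3.7% |
| 75% | 94.0% | 23% |
| 50% | 96.0% | 72% |
| 20% | 98.4% | 99.8% |

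A constant failure hazard is one case within this range: 0.92^(9/24) = 96.9% apparent, and a 91% chance of passing.

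**4. Effect of later PSAs.** Suppose the analysis waits for the last man's month 24, accrual is uniform over 24 months, and annual PSAs continue. Follow-up then runs evenly from 24 to 48 months. Half the men reach month 36, and essentially none are past month 48. As an illustration, spread first rises evenly over months 3 to 24. The seen share rises from 9/21 to (9 + 6 × 1/2)/21 = 12/21. The apparent rate falls from 96.6% to 95.4%, and the chance of passing from 85% to 57%. With 36 months of accrual (200 men at 5–6 a month take 33 to 40 months), two thirds reach month 36 and one third reach month 48. The share is then (9 + 4 + 2)/21 = 15/21, the apparent rate 94.3% and the chance 29%. The bias shrinks but does not vanish.

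**The case against.** The strongest reply is that Phoenix is plainly meant to decide. It is the only rule written beside the objective, the 92% comes from Phoenix results, 6.4.1 prefers it as more sensitive and specific, and ASTRO is kept for comparison with earlier literature. On that reading the ASTRO bias never reaches the pass rule. This is a fair reading and the most likely intent, but 7.3.1.2 does not commit to it. The reported ASTRO rate, itself part of the primary objective, would still be too high.

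Several stronger readings are tempting, and the documents do not support them:

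- **That efficacy is judged on both definitions.** Both are named as primary, but no section says both must pass or that either suffices. The fault is the silence.
- **That ASTRO cannot register any failure dated after month 9.** Section 6.4.1.2 also counts salvage therapy as failure, without three rises. The limit applies to rises alone. Salvage recovers only men so treated, and has no dating rule of its own.
- **That every man's data stop at month 24.** No cut-off is stated. Early enrollees may have later PSAs, as step 4 allows, though footnote b makes those visits optional. Ascertainment would then depend on enrolment date.
- **That the bias has one known size.** An even spread of first rises gives 85% with no later PSAs, but nothing in the plan supports that or any other timing.
- **That a series cited in the Background demonstrates the bias.** It reports "4-year PSA nadir + 2 FFBF was 90%, and ASTRO (three rises) FFBF was 70" (both percentages). There ASTRO is the lower of the two, at 4 years and in 40 men given a different dose. It shows that the definitions can differ widely, not that ASTRO is inflated at 2 years. The same section reports another series, at this protocol's prescription dose, with no failure under either definition.
- **That cancelling reversed rises is a further bias.** It is part of the written definition. It means only that a run ending at month 24 stays provisional until a later PSA.

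**Conclusion.** The point holds in two parts. As a matter of text, 7.3.1.2 leaves the deciding definition unnamed. As a matter of arithmetic, a 2-year ASTRO rate based on PSA rises through month 24 omits failures dated months 15 and 21, and so is biased upward unless salvage therapy or later PSAs reveal them.

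The consequence for the efficacy decision is conditional. If Phoenix supplies p, this bias does not affect it. If ASTRO does, with no salvage and no PSA after month 24, a treatment truly at 92% passes between about 23% and 99.8% of the time for assumed early shares of 75% down to 20%, against 3.7% with full ascertainment. Later PSAs in early enrollees would reduce this. The direction and the month-9 limit are firm; the size rests on assumed failure timing.

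**What to change.** State in 7.3.1.2 that p is the Phoenix bDFS proportion and that Phoenix alone decides whether the treatment is called effective. This matches the origin of the 92% benchmark. Report ASTRO bDFS descriptively, outside the pass rule. Estimate its 2-year rate only once the PSAs able to confirm rises starting by month 24 are in, which is month 48 on the annual schedule. State the data cut-off for that estimate, and add a dating rule for failures declared through salvage therapy.

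The optional follow-up after year 2 in footnote b of section 6.0 and the at-least-5-year follow-up in 2.1 must be reconciled, because the ASTRO estimate depends on those PSAs being collected.

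The cost is mainly wording, plus a later ASTRO figure. If follow-up after year 2 is in practice optional, securing the confirming PSAs is a further cost. The Phoenix decision at 2 years is not delayed.

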### Objectives

The *primary* objectives of this study are:

- To determine, in both low-risk and intermediate-risk cohorts, the rates of acute and late grade 3 or higher gastrointestinal and genitourinary toxicity observed during an initial 24 month follow up.
- To estimate the rate of biochemical Disease-Free Survival (bDFS), Phoenix and ASTRO definitions, at 2 years following hypofractionated SBRT for low and intermediate risk prostate cancer. Failure occurs when the PSA is  $\geq 2$  ng/ml more than the lowest PSA measurement before the current one, with no backdating.

The *secondary* objectives of this study are to:

To determine

1. the rate of local failure: proportion of patients with local disease progression at 2 years
2. rate of distant failure: proportion of patients with metastatic disease at 2 years
3. rate of disease-free survival: median time from start of treatment until disease progression
4. rate of disease-specific survival: death due to prostate cancer (excludes patients that relapse with inactive disease)
5. overall survival: median length of time from either the date of diagnosis or the start of treatment for a disease, such as cancer, that patients diagnosed with the disease are still alive.
6. quality of life (QOL) in generic and organ-specific domains using the FACT-G assessment tool

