##### 6.4.3.1 **DISTANT FAILURE** (includes regional failure)

documented if clinical, bone scan, CT or other imaging study shows metastatic disease. Biochemical failure with a negative prostate biopsy shall be considered distant only failure. Biopsy of metastatic site required if radiographic or clinical findings are equivocal. Type of metastatic failure (distant and/or regional) shall be recorded if known.

Prostate biopsy recommended at this time.

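### PSA failure with a negative biopsy counts as distant failure without shown metastasis, and an early positive biopsy has no category, so the 2-year rates can overstate distant and understate local failure

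*Combined protocol and SAP*

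**What the plan says.** The endpoints are set out in the Protocol Summary (Objectives) and repeated in Section 7.3: "the rate of local failure: proportion of patients with local disease progression at 2 years" and "rate of distant failure: proportion of patients with metastatic disease at 2 years".

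Section 6.4.2 gives two routes to local failure.
- Clinical: "failure includes a palpable abnormality that has increased in size, failure of regression of a palpable abnormality by 2 years after treatment", or an abnormality that reappears after complete response. This route has no minimum time. "Patients with clinical failure and no biopsy are" to be counted as local failures.
- Histologic: "Histologic criteria for local failure is a positive prostate biopsy more than 2 years after treatment".

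The same section states who is free of local failure: "Patients with a normal exam and no evidence of PSA failure shall be considered controlled locally".

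Section 6.4.3.1 accepts metastatic disease found clinically or on imaging as distant failure, and then adds: "Biochemical failure with a negative prostate biopsy shall be considered distant only failure". That addition has no time limit.

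On timing, Section 6.1.5 says "PROSTATE BIOPSY will be performed at time of biochemical or local clinical failure". Footnote a in Section 6.0 requires biopsy at documented failure and also recommends one at 2 years if failure is suspected. Section 6.1.6 schedules a bone scan at biochemical failure. Section 6.4 counts intervals from the first treatment.

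Section 7.3.2.1 says the local and distant rates will be quantified from repeated PSA levels by GEE. It mentions neither biopsy nor imaging.

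**The concern.** The same early biopsy is treated in opposite ways according to its result. If negative, it decides the case and makes the PSA failure distant. If positive, it does not meet the histologic criterion until more than 2 years have passed, which is after the landmark at which the endpoint is read. If the 2-year limit reflects doubt about early biopsies, that doubt does not explain relying on early negatives.

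The distant rule also conflicts with the objective it serves. A man whose bone scan at PSA failure is clear and whose prostate biopsy is negative has no demonstrated metastasis, yet he enters a rate defined as metastatic disease.

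At stake is the 2-year pattern of failure, which comprises two named secondary objectives. Few failures are expected, so placing a handful of men in the wrong group, or in none, could change most of that result.

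**Working it through.** The documents state no expected local or distant failure rate, so there is no figure to reproduce. The check has two parts.

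**1. Applying the rules.** Take a man with PSA failure by 2 years and no metastasis on imaging.

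| Exam | Biopsy | Class under Sections 6.4.2 and 6.4.3.1 |
|---|---|---|
| Normal | Negative, any time | Distant only |
| Normal | Positive, at or before 2 years | None |
| Normal | Positive, after 2 years | Local (histologic); entry into the 2-year proportion not stated |
| Clinical failure | None | Local (clinical) |
| Clinical failure | Positive, at or before 2 years | Not spelled out; nothing bars counting it as clinical failure |

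The second row has no class for four reasons. Local control requires no PSA failure. The histologic criterion requires more than 2 years. The clinical route requires an abnormal exam. The distant-only rule requires a negative biopsy.

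**2. Size, as a scenario only.**

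Inputs from the documents: N = 200 (Section 7.2.3); bDFS of 97% and 96% as assumed SBRT rates and 92% as the performance criterion (Section 7.2.2).

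Assumptions not in the documents:
- the biopsy-positive share q is 25–75%;
- every PSA failure has a normal exam, is biopsied by 2 years and shows no metastasis on imaging;
- the bDFS figures apply at 2 years, although the 92% is a 5-year figure and the SBRT rate is argued from 5-year HDR results.

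Formulas: PSA failures F = 200 × (1 − bDFS). Positive biopsies that cannot count as local = F × q. Negative biopsies counted as distant = F × (1 − q). Dividing by 200 gives percentage points.

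| bDFS | F | Positives not counted, q = 25% to 75% | Negatives counted as distant, q = 25% to 75% |
|---|---|---|---|
| 97% | 6 | 1.5 to 4.5 men (0.75 to 2.25 points) | 4.5 to 1.5 men (2.25 to 0.75 points) |
| 96% | 8 | 2 to 6 men (1 to 3 points) | 6 to 2 men (3 to 1 points) |
| 92% | 16 | 4 to 12 men (2 to 6 points) | 12 to 4 men (6 to 2 points) |

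The overall range for either rate is 0.75 to 6 points. The two shifts trade off: together they equal the PSA failure rate (for example 0.75 + 2.25 = 3 points at 97%), so both cannot be at their maximum at once.

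**The case against.** Several points on the other side have force.

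- A reader might infer that no positive biopsy can ever count as local failure at 2 years. The documents do not support that. The lead definition in Section 6.4.2 is clinical, has no 2-year minimum, and does not exclude a man with clinical failure who also has an early positive biopsy. Only the purely histologic route is closed.
- A reader might also infer that early positive biopsies are moved into distant failure. They are not; they are left unclassified. The distant over-count comes from the separate negative-biopsy rule.
- A biopsy prompted by the 24-month visit may fall just after 2 years. No window says whether it enters the 2-year proportion. Hence the histologic route contributes essentially nothing, rather than strictly nothing.
- It is tempting to say that any transient PSA rise with a negative biopsy becomes a distant failure. That can happen under the Phoenix definition. The ASTRO definition in Section 6.4.1.2 excludes three rises in the first 2 years followed by a non-hormonal decline, and Section 6.4.3.1 does not say which definition applies.
- Section 7.3.2.1 plans GEE on PSA levels, so it is unclear whether these rules will drive the reported rates. This stands, but PSA alone cannot separate local from distant failure. The two sections need reconciling in any case.
- The bone scan at PSA failure and the recorded type of metastatic failure would allow shown and inferred distant failures to be separated. This limits the harm to labelling and makes the repair cheap, but the plan does not call for that separation.
- The endpoints are secondary and descriptive, with no hypothesis or power attached. That limits the weight of the point; it does not remove the contradiction.

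**Conclusion.** The concern holds in a limited form. Section 6.4.3.1 contradicts the objective's definition of distant failure and can overstate it. Section 6.4.2 leaves PSA failures with a normal exam and an early positive biopsy without a category, so local failure at 2 years can be understated.

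The size is not derivable from the documents. The 0.75 to 6 point range rests on the assumed biopsy-positive share and on the exam, biopsy and imaging assumptions listed above. A reader should not conclude that the pattern of failure is certainly skewed or that a known number of men will be misclassified.

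Primary bDFS and the toxicity endpoint are unaffected. The definitions should be corrected because the conflict is in the text and the data needed are already planned.

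**What to change.** 1. Define distant failure as metastatic disease shown clinically, on imaging or by biopsy of the metastatic site, in line with the objective.
2. Report PSA failure with a negative prostate biopsy and no shown metastasis as a separate biochemical-only category.
3. Report PSA failure with a positive biopsy at or before 2 years as its own category beside the local-failure rate.
4. State whether a biopsy prompted by the 24-month visit but taken after 2 years enters the 2-year proportion, and which PSA-failure definition governs these categories.
5. Reconcile Section 7.3.2.1 with Sections 6.4.2 and 6.4.3.1, so that the analysis uses the classified events.

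Moving the landmark later would not be enough. A man with a positive biopsy at 18 months would still fail the histologic criterion without another biopsy. Follow-up is also stated unevenly: at least 5 years in Section 2.1, but optional after 2 years in footnote b of Section 6.0.

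The cost is one or two extra reporting categories and less direct comparability with series that use the negative-biopsy convention. No new procedure is needed.
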